Version Number: 5 Version Date: 6/14/21

Change:

• The schedule of questionnaires was updated, and participant compensation was updated.

PRÉCIS

Study Title

iQuit Mindfully: Mindfulness-based Smoking Cessation Enhanced with Mobile Technology

Objectives

Aim I: Test the efficacy of a mindfulness-based text messaging program for smoking cessation ("iQuit Mindfully"), both as a standalone intervention and in combination with in-person counseling. Aim II: Investigate the mechanisms through which mindfulness training impacts smoking cessation.

Design, Interventions and Outcomes

This study is a 2 X 2 randomized controlled trial to investigate the effects of the iQuit Mindfully text messaging program, both as a standalone intervention and in combination with in-person counseling (Mindfulness-based Addiction Treatment; MBAT), compared to usual care. Participants will be randomized to one of four groups based on assignment to iQuit Mindfully text messages (yes/no) and in-person MBAT (yes/no):

- Usual Care (self-help materials + nicotine patch treatment)
- MBAT (8 weekly virtual MBAT sessions + self-help materials + nicotine patch treatment)
- iQuit Mindfully (iQuit Mindfully text messages + self-help materials + nicotine patch treatment)
- MBAT + iQuit Mindfully (8 weekly virtual MBAT sessions + iQuit Mindfully text messages + self-help materials + nicotine patch treatment)

All study participants will receive self-help smoking cessation materials, including the "Clearing the Air" booklet developed by the National Cancer Institute (NCI) and a referral to the Tobacco Cessation Quitline ([name]). All study participants will also receive nicotine patches. Assessments will occur at baseline and weeks 1, 3, 5, 8, 12, and 24. Primary outcomes are smoking abstinence at 8 weeks after the start of treatment (7-day abstinence, biochemically verified by expired carbon monoxide <6 ppm), 12 weeks after the start of treatment (3 month follow-up; 7-day abstinence, biochemically verified by expired carbon monoxide <6 ppm), and 24 weeks after the start of treatment (6-month follow-up; 7-day abstinence, biochemically verified by saliva cotinine < 20 ng/ml). Secondary outcomes include frequency of home mindfulness practice and self-reported levels of mindfulness, emotions, craving, withdrawal, dependence, self-efficacy, and social support.

Sample Size and Population

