1. STUDY OBJECTIVES

Study aims are to test the efficacy of a mindfulness-based text messaging program for smoking cessation ("iQuit Mindfully"), both as a standalone intervention and in combination with in-person counseling, and examine underlying mechanisms of mindfulness treatment. Approximately 485 participants (maximum 500) will be randomized to one of four groups:

- Usual Care (self-help materials + nicotine patch treatment)
- MBAT (8 weekly virtual MBAT sessions + self-help materials + nicotine patch treatment)
- iQuit Mindfully (iQuit Mindfully text messages + self-help materials + nicotine patch treatment)
- MBAT + iQuit Mindfully (8 weekly virtual MBAT sessions + iQuit Mindfully text messages + self-help materials + nicotine patch treatment)

All study participants will receive self-help smoking cessation materials, including the "Clearing the Air" booklet developed by the National Cancer Institute (NCI) and a referral to the Tobacco Cessation Quitline ([name]). All study participants will also receive nicotine patches. Assessments will occur at baseline and weeks 1, 3, 5, 8, 12, and 24. Primary outcomes are smoking abstinence at 8 weeks after the start of treatment (7-day abstinence, biochemically verified by expired carbon monoxide <6 ppm), 12 weeks after the start of treatment (3 month follow-up; 7-day abstinence, biochemically verified by expired carbon monoxide <6 ppm), and 24 weeks after the start of treatment (6-month follow-up; 7-day abstinence, biochemically verified by saliva cotinine < 20 ng/ml). Secondary outcomes include frequency of home mindfulness practice and self-reported levels of mindfulness, emotions, craving, withdrawal, dependence, self-efficacy, and social support. Aims and hypotheses are outlined below:

Aim I. Test the efficacy of a mindfulness-based text messaging program for smoking cessation ("iQuit Mindfully"), both as a standalone intervention and in combination with in-person counseling.

We hypothesize that:

- 1a) MBAT + iQuit Mindfully will result in higher rates of smoking cessation and lapse recovery than MBAT, which will produce higher cessation and lapse recovery than UC. iQuit Mindfully as a standalone intervention will also produce higher cessation and lapse recovery than UC.
- 1b) As an exploratory aim, we will examine whether poverty status moderates treatment efficacy (i.e., poverty status will predict worse cessation outcomes in MBAT but not MBAT + iQuit Mindfully).

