9. STATISTICAL CONSIDERATIONS AND DATA ANALYSES

We will conduct both intent-to-treat (ITT) and per protocol analyses. ITT includes all participants that were randomized, regardless of compliance, withdrawal, and other events after randomization. A strength of ITT is that it is based on original randomization. However, effect estimation using ITT may be conservative and misleading with increasing attrition. Per protocol analysis considers only participants who fully complied and completed the study. Per protocol is less conservative and may reflect true treatment differences for those with full compliance. Including both approaches will provide a more complete understanding of treatment effects.

Analyses will be performed using SAS. Descriptive statistics for all measurements will be reported. Frequency distributions will be created to screen for any coding or entry errors. Frequency distributions summarize categorical data, and measures of central tendency and dispersion will summarize continuous data. All data will be examined for bivariate relationships with the outcomes and with each other. All analyses will control for demographics (age, gender, race/ethnicity, education level, partner status) and baseline nicotine dependence (cigarettes per day and time to first cigarette). The overall study level of significance will be α =.05.

Aim I. Test the efficacy of a mindfulness-based text messaging program for smoking cessation ("iQuit Mindfully"), both as a standalone intervention and in combination with virtual counseling.

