The relationship between treatment condition and each dichotomous study outcome (smoking cessation, lapse recovery) will be assessed with a generalized linear mixed model (GzLMM) with a Binomial distribution and logit link function. This is an appropriate statistical model with repeated measures data collected over time. ⁴⁴ A 2-level multilevel GzLMM will be specified, with time nested within subject. This approach will properly account for the multilevel data structure. Fixed effects considered in each model will include demographics, baseline nicotine dependence, treatment condition and time as main effects, and a treatment condition by time interaction. Testing of covariance structure will be conducted, and information criteria will be used to assess model fit and selection. Linear contrasts will be built into the analysis to estimate specific comparative effects of all treatment conditions. To test treatment effects on primary smoking cessation outcomes, repeated measures outcomes will be biochemically-confirmed 7-day point prevalence abstinence at weeks 8, 12, and 24. To test treatment effects on lapse recovery, this analysis will also be conducted among participants classified as smoking at the last treatment session. ¹² In addition, gender and race/ethnicity will be assessed as potential moderators of treatment effects.

The moderating effect of poverty status will be examined with the addition of a poverty status by treatment condition interaction into the models described in 1a). This will be tested using both dichotomous (i.e., below vs. at or above federal poverty threshold) and continuous poverty status variables (i.e., depth of poverty as indicated by income-to-poverty ratio and income deficit/surplus) according to U.S. Census guidelines.^{45,46}

Aim II. Investigate the mechanisms through which mindfulness training impacts smoking cessation.

Hypotheses regarding mechanisms will be tested with both traditional questionnaire data (collected from baseline through 24 weeks after the start of treatment) and electronic diary data (collected for 6 continuous weeks during treatment), separately. Mediation testing will be conducted regardless of statistical significance of intervention effects because of statistical, conceptual, and practical reasons for testing mediation in such cases.⁴⁷ Volatility will be calculated using the mean square successive

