Power and Sample Size Determination. Sample size was estimated based on the number of participants needed to detect meaningful treatment effects of the iQuit Mindfully and MBAT interventions. We obtained effect sizes (converted to Cohen's *d* for comparability across measures) from relevant meta-analyses and used the Optimal Design program to estimate sample size for GzLMM models. Samoking abstinence in MBIs vs. UC was quantified as *d*=0.35 in a meta-analysis, and a Cochrane review of primarily text messaging-based interventions for smoking cessation concluded an effect size of *d*=0.33. Assuming 80% power, level of significance of .05, two-tailed statistical tests, error variance of 1.0, coefficient variance of 2.0, and oversampling to account for 20% attrition, this results in 145 participants in each treatment group. An unequal allocation ratio was used to allocate fewer participants to usual care (*n*=50), 55,56 for an overall sample size of 485 participants (145 per treatment group and 50 in usual care). We expect this sample size to adequately allow for mediational testing (Aim 2) at the 80% power level. Fritz and MacKinnon for offer a guide regarding sample size required to detect mediated effects and report that 79.9% of studies in their literature review applied mediational testing with less than 400 subjects, suggesting our study plan with 485 subjects will be ample for achieving all study aims.

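### The plan sets an overall study significance level of .05 but gives no procedure that delivers it across three hypothesised contrasts and three primary visits

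*Combined protocol and SAP*

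**What the plan says.** - **Level.** Section 9, among the general conventions: "The overall study level of significance will be α =.05".
- **Contrasts.** Hypothesis 1a in section 1 begins "MBAT + iQuit Mindfully will result in higher rates of smoking cessation and lapse recovery than MBAT", then places MBAT above usual care (UC), and separately places standalone iQuit Mindfully above UC. That makes three contrasts. Only the poverty moderation (1b) is labelled exploratory.
- **Visits.** In the Précis and sections 1 and 3, "Primary outcomes are smoking abstinence at 8 weeks after the start of treatment", and weeks 12 and 24 follow in the same list. No visit is ranked above another.
- **Model.** Under Aim I in section 9, each dichotomous outcome "will be assessed with a generalized linear mixed model (GzLMM) with a Binomial distribution and logit link function", with treatment, time and their interaction. For cessation, "repeated measures outcomes will be biochemically-confirmed 7-day point prevalence abstinence at weeks 8, 12, and 24". The inference is described only as "Linear contrasts will be built into the analysis to estimate specific comparative effects of all treatment conditions".
- **Sizing.** Section 9, power paragraph: "Assuming 80% power, level of significance of .05, two-tailed statistical tests". The level is not divided.
- **Analysis sets.** Section 9 runs both intent-to-treat (ITT) and per-protocol analyses and does not say which decides.

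**The concern.** A level set for the whole study implies a rule for combining the tests that can declare success. Section 9 has no multiplicity adjustment, testing order, gatekeeping test, lead contrast or choice between a time-averaged contrast, one visit and each visit. The only per-test level anywhere is the undivided .05 used for sizing. A reader therefore cannot tell which result decides Aim I or check the stated level, and the deciding contrast, visit or analysis set could be picked after the data are seen.

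**Working it through.** **The plan's own figure.** For two means, n per arm = 2(z₀.₉₇₅ + z₀.₈₀)²/d² = 2(1.960 + 0.842)²/0.33² = 144.1, so 145. The planned group size is what an undivided two-sided .05 gives at d=0.33 for one contrast. This is the figure before attrition, although the plan says "oversampling to account for 20% attrition, this results in 145 participants in each treatment group"; that mismatch is a separate matter. What counts here is that no allowance for several contrasts is visible.

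**Inputs for the error calculation.** Arms of 50 (UC) and 145 in each of the other three (section 9); three contrasts (hypothesis 1a); each tested at |z| > 1.96 (assumed, from the sizing level); no true effect anywhere; success means at least one significant contrast (assumed).

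**Correlations between contrasts.** The variances are proportional to 1/145 + 1/145 = 0.01379 for MBAT + iQuit vs MBAT, and 1/50 + 1/145 = 0.02690 for each comparison with UC.
- MBAT + iQuit vs MBAT, with MBAT vs UC: −(1/145)/√(0.01379 × 0.02690) = −0.358
- MBAT vs UC, with iQuit vs UC: (1/50)/0.02690 = 0.744
- MBAT + iQuit vs MBAT, with iQuit vs UC: 0

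**One time summary, normal approximation.** Simulating the joint distribution gives 12.4% two-sided and 6.5% for a false win in the favourable direction. Three independent tests would give 1 − 0.95³ = 14.3%. Taking 20% off every arm (40/116/116/116) leaves the result essentially unchanged.

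**One time summary, binary outcome.** The documents give no UC abstinence rate, so 5%, 10% and 20% are assumed. Overall two-sided error:

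| Test | Arms | 5% | 10% | 20% |
|---|---|---|---|---|
| Single-visit logit Wald | planned | 8.1% | 9.2% | 11.5% |
| Single-visit logit Wald | 20% attrition | 6.8% | 8.4% | 11.2% |
| Mixed model, time-averaged | planned | 8% | 11-12% | 12-13% |
| Mixed model, time-averaged | 20% attrition | 7.5% | 9-10% | 12% |

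The mixed model is a random-intercept logit with arm-by-visit terms and assumed intercept SDs of 2 and 3.5. It has no covariates and no imputation, so it approximates the planned model. The low values at 5% come from Wald tests being conservative when the UC arm has few events. A single-visit score test at 5% gives about 11% (planned arms) and 10% (attrition).

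**Each visit tested (nine tests).** The normal approximation gives 20% to 33% two-sided as the assumed between-visit correlation falls from 0.9 to 0. The mixed model gives 17-30% over the assumed abstinence rates. The combined range is about 17-33%.

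**All three must win.** Under the same null, all three contrasts are significant in the favourable direction in well under 0.1% of trials.

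**The case against.** The level sits beside software, descriptive statistics and covariates, so it may mean only the level used throughout, which would agree with the sizing. On that reading the fault is wording, and whether a multi-arm trial of distinct interventions needs adjustment is partly a matter of judgement. This stands as a possible reading, but the sentence speaks of the overall study, and the text must be changed to say otherwise.

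Hypothesis 1a can also be read as one ordered pattern. If support required every contrast to win, testing each at .05 would not inflate the error. An omnibus test across the arms before the contrasts would likewise hold the error at about 4% when nothing works. Both are sound rules, but the plan states neither, nor does it state that one win is enough.

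A reader might infer that the trial's false-positive rate is 20% or 30%. The documents do not support that: it needs each visit to be tested separately, and the single repeated-measures model is equally compatible with one time-averaged contrast. Nor do they support a flat 12% for the fitted analysis, because the size depends on the abstinence rate and on the test statistic, and neither is given.

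**Conclusion.** The gap is real and should be closed: an overall level is claimed and nothing in the plan produces it. That does not depend on any simulation. The size is conditional. With each contrast at two-sided .05, any single win counting and one time summary, the overall two-sided error under no effect is about 12% by normal approximation (about 6.5% favourable). It is about 7-9% for single-visit Wald tests at an assumed 5-10% abstinence. If each visit were tested it would be about 17-33%, under assumed rates and correlations. A rule that all contrasts must win would remove the inflation, but the plan would have to state it. Lapse recovery and the per-protocol repeat of each test are not counted in these figures.

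**What to change.** In the opening paragraphs of section 9 and under Aim I:

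1. Name ITT as the deciding analysis and per-protocol as supportive.
2. Name one deciding time summary: a single visit, or the time-averaged contrast from the planned model. The average would pool CO verification (weeks 8 and 12) with cotinine (week 24), and the plan should acknowledge this. Alternatively, keep all three visits primary and include them in the adjustment; with nine tests Holm would start at .05/9 = .0056.
3. Test the three hypothesis-1a contrasts at overall two-sided .05, in a pre-stated fixed sequence or with Holm.
4. Label the remaining contrasts and lapse recovery secondary, and say that the .05 covers the Aim I primary cessation contrasts.

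If the sponsor means .05 per comparison, it should say so and remove the reference to the overall study. That costs no power but gives up the overall claim.

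**Cost.** The edit is wording only, but adjustment lowers power. By the two-mean formula, power = Φ(d/√(1/n₁ + 1/n₂) − z). At d=0.33, Holm's first step (.05/3 = .0167, z = 2.394 instead of 1.960) gives:

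| Comparison | At .05 | At .0167 |
|---|---|---|
| 145 vs 145 | 80% | 66% |
| 145 vs 50 | 52% | 35% |
| 116 vs 116 (20% attrition) | 71% | 55% |
| 116 vs 40 (20% attrition) | 44% | 28% |

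A fixed sequence keeps the first contrast at full .05 and moves the cost to later ones. With the plan's effects (0.35 for MBAT, 0.33 for texts, assumed additive) and 20% attrition, power for MBAT + iQuit vs MBAT / MBAT vs UC / iQuit vs UC is 71/48/44% unadjusted, 71/29/22% in a fixed sequence in that order, and 60/37/34% with full Holm. These are two-mean approximations, not the plan's repeated-measures calculation.

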For our previous smoking cessation study at GSU, the inclusion criteria were slightly more rigid. For example, interested individuals were excluded if they also used tobacco products other than cigarettes. Given that use of other tobacco products (e.g., cigars, little cigars, cigarillos) is common among low-income adult smokers, we believe it is important to include these people and help them quit smoking cigarettes as well as other tobacco products. Accordingly, we will contact individuals who expressed interest in our previous smoking cessation study and did not qualify at that time but might meet the current eligibility criteria. We will describe the current study and if they are interested, they will complete the same screening procedures as other potential participants.

Randomization. Randomization will take place at the end of the baseline session, after baseline assessments have been administered. Stratified permutated block randomization will be implemented. Block randomization can achieve balance in the number of assignments to each treatment group. This form of randomization can be conducted within each stratum (i.e., stratified permutated block design) in efforts to achieve both covariate balance and treatment balance. To Given the dangers of overstratification (e.g., with too many strata, there may be insufficient numbers of participants within each block), researchers have recommended using one or two stratification variables that are expected to be most strongly associated with the outcome. To Stratification will be conducted with respect to race/ethnicity and poverty status, both of which are predictors of smoking cessation success.

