MBAT Treatment (MBAT and MBAT + iQuit Mindfully conditions). Participants in the MBAT and MBAT + iQuit Mindfully conditions will receive virtual group counseling based on the Mindfulness-Based Addiction Treatment (MBAT) group protocol. 19 [name] (certified mindfulness-based stress reduction teacher and licensed professional counselor), [name] (certified mindfulnessbased stress reduction teacher and licensed clinical social worker) and/or their trained colleagues will lead MBAT sessions. MBAT closely follows Mindfulness-based Cognitive Therapy (MBCT) procedures, but replaces the depression-related material with nicotine dependence-related material. MBAT consists of 8 weekly 2-hour sessions. The core aims are to: 1) become more aware of thoughts, feelings, and sensations from moment to moment, 2) develop a different way of relating to thoughts, feelings, and sensations, and 3) obtain the ability to disengage attention and choose skillful responses to thoughts, feelings, and situations. Participants are encouraged to choose their own quit date between day 7 and day 30 of the program. Sessions 1-4 concentrate on learning how to direct and focus attention. Participants become aware of how little attention is usually paid to activities in their daily life ("automatic pilot"). Next, they learn how to not only notice that the mind is wandering, but to bring it back to focus on the breath. Participants learn how a wandering mind can increase negative thoughts and feelings (e.g., fantasies about smoking can lead to feelings of anger about being deprived). Engaging in these thoughts can escalate to severe craving such that it becomes more difficult to enact purposeful, adaptive responses. By bringing attention back to the present, one can disengage from unhelpful thoughts and deal with the situation more flexibly (e.g., one could note

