that craving is a sensation as opposed to an imperative and notice it nonjudgmentally until it passes, choose to engage in a coping behavior, or bring attention back to the breath). MBAT emphasizes daily practice in several forms: sitting meditation, body scan meditation, walking meditation, eating meditation, and gentle yoga. Each of these practices share a focus on awareness of the breath. By offering a menu of practices, differing preferences and learning styles can be accommodated. Sessions 5-8 focus on continued development of awareness of the present, along with expansion of techniques for dealing with thoughts, feelings, and situations.

Zoom group sessions will be audio and video recorded. These recordings will be used to assess treatment fidelity. Also, if a group member is unable to attend a session they may make it up by watching the video recording. They will only be able to do this by making an appointment with study staff, who will play the recording while on Zoom with the participant.

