- The Mindful Attention Awareness Scale MAAS; ³⁷ is a 15-item self-report measure of dispositional mindfulness that has shown good reliability and validity.³⁷
- The Five-Facet Mindfulness Questionnaire-Short Form³⁸ is a 24-item self-report questionnaire of facets of dispositional mindfulness. The scale yields five factors: 1) Nonreactivity, 2) Observing, 3) Acting with Awareness, 4) Describing/Labeling with Words, and 5) Nonjudging of Experience, with strong psychometric properties.
- The Self-Compassion Scale Short Form⁴⁵ is a 12-item self-report measure of self-compassion. Subscales include self-kindness, self-judgement, common humanity, isolation, mindfulness, and over-identification.⁴⁵
- Participants will fill out a *Mindfulness Practice Log*¹² to indicate how frequently they practice each of the mindfulness techniques taught in treatment.
- The *Perceived Stress Scale*³⁹ is a 10-item self-report measure of the extent to which individuals view their lives as stressful. The scale shows good psychometric properties.
- The Positive and Negative Affect Schedule (PANAS ⁴⁰) is a 20-item self-report measure of affective experience yielding two factors (Positive and Negative Affect) with strong psychometric properties ⁴⁰.
- The *Multidimensional Scale of Perceived Social Support*⁴¹ is a 12-item scale, with subscales assessing perceived social support from family, friends, and significant others.
- The *Group Climate Questionnaire* (*GCQ-S*)⁴⁸ is a 12-item self-report scale which measures climate and cohesion of the group (only applicable for MBAT participants). Sub-scales include engaged, conflict, and avoiding.⁴⁸
- Participants will be asked to provide feedback about their experiences receiving the text messages (Text Message Feedback).

- Participants will complete 4 items to indicate perceived benefits of the quit smoking program. As described by Hoeppner et al. (2017),⁴² participants rate the extent to which the program gave them confidence to quit smoking, made them think that it was worthwhile to quit, made them feel that someone cared if they quit, and made them feel that they knew the right steps to take to quit. Items are rated from 1 (completely disagree) to 5 (completely agree).

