- Participants will complete *Program Evaluations* to provide for their feedback about and suggestions for improving the intervention (both MBAT and iQuit Mindfully text messages). Usual care participants will answer 1 program evaluation question: "On the scale below, please circle the number that best represents whether you would recommend this quit smoking program (or something similar) for others who are interested in quitting smoking." (rated on 1-10 scale).

The maximum time between telephone screening and enrollment will be 1 month. The maximum time between baseline assessment and start of treatment will be 1 month. However, we will employ a variety of strategies to ensure that these timeframes are as short as possible. For example, in order to reduce the time between telephone screening and baseline we will offer a variety of days and times for baseline assessment. We will also time our recruitment efforts around planned baseline assessments to maximize potential participants' interest (in order to prevent longer wait time to accrue a sufficient number of participants to start a group).

Electronic Diary Assessments. *Electronic Diary Assessments* (also referred to as short-surveys) will be administered in the evening on every other day from Week 2 to Week 8, thus capturing key processes surrounding quitting smoking. Diary assessments will assess smoking behavior ("How many cigarettes did you smoke today?") and each of the hypothesized mechanisms (mindfulness, emotions, craving and withdrawal, self-efficacy, and social support). Participants will also indicate their mindfulness practice that day (See Appendix). Participants will receive an email and/or text with the REDCap link to the electronic diary assessment survey. Both participant-initiated options allow respondents to complete assessments at a time that is convenient to them between that evening and the next morning (by 9am).

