 pilot study virtual sessions, some participants did not have a private place to join. Being able to
 use a tablet in a private room at GSU would provide a solution.
- MBAT participants will attend a group Zoom orientation within two weeks before the first treatment session. This will give them a chance to meet each other, practice using Zoom together (e.g., muting/unmuting, turning camera on and off), and ask questions of the study staff.

- When participants connect to Zoom, study staff will admit them individually into a separate breakout room to ensure that they are in a private location and troubleshoot any issues.
- We will encourage participants to join Zoom sessions a few minutes early so that they have a chance to get to know their fellow group members better.
- Both mindfulness instructors (certified Mindfulness-Based Stress Reduction teachers through the University of Massachusetts Medical School) have experience leading online mindfulness groups through Zoom and will draw on their past experience. For example, they will encourage participants to stay unmuted during discussion to facilitate natural conversation (unless there is excessive background noise); mute participants during mindfulness practices; and provide brief breaks.

*GSU continues to update guidelines for on-campus research. We will follow updated guidelines as they become available.

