By virtue of participating in a treatment group with other people, participants' verbal responses during MBAT treatment will be known to others in the group. Thus, we will request (in the consent form and verbally at the start of the group) that participants keep what they hear confidential. Of course, we cannot guarantee that the other members of the treatment group will maintain confidentiality of responses, and this is made clear in the consent form.

Study Discontinuation

The study may be discontinued at any time by the IRB, NCI, or other government agencies as part of their duties to ensure that research participants are protected.

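### MBAT is delivered in groups in two of the four arms, but the primary mixed model has no group level, so contrasts with an MBAT arm have mis-stated standard errors if outcomes within groups are correlated

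*Combined protocol and SAP*

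**What the plan says.** Randomization is individual (Section 4): "Randomization will take place at the end of the baseline session, after baseline assessments have been administered". Section 5 then states that participants in the MBAT and MBAT + iQuit Mindfully "conditions will receive virtual group counseling based on the Mindfulness-Based Addiction Treatment (MBAT) group protocol", in eight weekly two-hour sessions. Section 6.2 shows that groups are assembled as cohorts; recruitment is timed "in order to prevent longer wait time to accrue a sufficient number of participants to start a group".

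Other sections show that members interact:
- Of the pre-treatment Zoom orientation, Section 6.2 says "This will give them a chance to meet each other, practice using Zoom together".
- The Group Climate Questionnaire "is a 12-item self-report scale which measures climate and cohesion of the group (only applicable for MBAT participants").
- Section 11 warns that participants' "verbal responses during MBAT treatment will be known to others in the group".

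The primary model in Section 9 (Aim I) has two levels: "A 2-level multilevel GzLMM will be specified, with time nested within subject. This approach will properly account for the multilevel data structure". The same paragraph plans contrasts among all four conditions. The covariance testing, the imputation model, the Aim II bootstrap and the sample-size paragraph mention no group term, ICC or design effect. The schedule in Section 6.1 puts both MBAT arms on one row and does not say whether they meet together.

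**The concern.** A subject effect captures correlation between one person's visits. It does not capture correlation between different people who sat in the same group. Groups exist in two arms and not in the other two, so the design is partially nested, and the adequacy statement overlooks that level.

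Hypothesis 1a (Section 1) names MBAT vs UC and MBAT + iQuit vs MBAT. If members' outcomes are correlated, the p-values and confidence intervals for both are off. For the second, even the direction of the error depends on something the plan leaves out. With separate groups, that contrast also has less power than planned.

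**Working it through.** **Inputs from the documents.** 145 participants in each of three arms and 50 in UC, 80% power, two-sided 0.05, 20% attrition (Section 9); enrolment over about 3 years (Section 4); at most 1 month from baseline to start of treatment (Section 6.2).

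**The plan's own figure.** The two-mean formula n = 2(1.96 + 0.842)²/d² gives 129 per arm at d = 0.35 and 145 at d = 0.33. Dividing by 0.8 for attrition gives 162 and 182. The stated 145 therefore matches d = 0.33 before attrition. A repeated-measures formula with undocumented scaling also gives about 144-145 after attrition, so I do not call 145 wrong. No variant contains a group term.

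**Assumed group size.** The two MBAT arms total 290. Steady accrual gives 290/36 = 8.1 a month, or 145/36 = 4.0 per arm. With the 1-month limit, that is about k = 4 members of one arm per start. After 20% attrition, 4 × 0.8 = 3.2 have observed outcomes.

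**Formulas.** The design effect is DE = 1 + (k − 1) × ICC. With R the ratio of true to model-based variance, true alpha = 2[1 − Φ(1.96/√R)].
- MBAT vs UC: R = (DE/145 + 1/50)/(1/145 + 1/50).
- MBAT vs text-only: R = (DE + 1)/2.
- MBAT + iQuit vs MBAT, separate groups: R = DE.
- MBAT + iQuit vs MBAT, shared and evenly mixed groups: R = 1 − ICC, because the group effect cancels.
- Power for the separate-group contrast, taking the plan's 80% as given: Φ(2.80/√DE − 1.96).

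**Results** at ICC 0.01 / 0.05 / 0.10:

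| | k = 4 | k = 3.2 |
|---|---|---|
| DE | 1.03 / 1.15 / 1.30 | 1.022 / 1.11 / 1.22 |
| MBAT vs UC, alpha % | 5.1 / 5.4 / 5.9 | 5.1 / 5.3 / 5.7 |
| MBAT vs text-only, alpha % | 5.2 / 5.9 / 6.8 | 5.1 / 5.6 / 6.3 |
| MBAT + iQuit vs MBAT, separate, alpha % | 5.3 / 6.8 / 8.6 | 5.3 / 6.3 / 7.6 |
| Same, shared, alpha % | 4.9 / 4.4 / 3.9 | 4.9 / 4.4 / 3.9 |
| Power, separate, % | 78.8 / 74.3 / 69.0 | 79.1 / 75.8 / 71.8 |

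MBAT vs UC moves little because the 50 ungrouped UC participants supply 74% (ICC 0.01) to 69% (ICC 0.10) of its variance at k = 4.

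**Larger groups.** If recruitment came in waves and separate groups held 8 to 12, the same formulas give 5.2-8.3% for MBAT vs UC and 5.8-17.6% for MBAT + iQuit vs MBAT. The top figure needs both 12 per group and ICC 0.10.

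**Simulation check.** A two-level mixed logit was fitted to 20,000 null trials per setting (arms 50/145/145/145, three visits, complete data, no covariates, assumed 20% abstinence, between-person variance 2.0; Monte Carlo standard error 0.15-0.27 points).
- ICC 0: 4.9% for both 1a contrasts.
- Separate groups of 4, ICC 0.01 / 0.05 / 0.10: MBAT vs UC 5.1 / 5.2 / 6.0%; MBAT + iQuit vs MBAT 5.4 / 6.8 / 8.7%.
- Shared groups, 4 per arm, ICC 0.05 / 0.10: 5.4 / 5.8% and 4.4 / 3.7%.
- iQuit vs UC: 4.7-5.2% in every setting.

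**The case against.** The strongest reply is that the harm is conditional on facts nobody has. ICC, group size and group composition are all undocumented. At ICC 0.01 the effect is negligible. In the simulation, ICC 0.10 corresponds to group membership explaining about 24% of between-person variance, which is a lot for a treatment that follows a set protocol with fidelity checks. Weeks 12 and 24 also fall well after the groups end, and the simulation let no group effect decay and omitted covariates and missing data. All of this stands, and it is why the result is a range with a low bottom end.

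A reader might infer that every MBAT comparison is seriously anti-conservative. The documents do not support that. MBAT vs UC stays at or below 5.9% in the base range, and clear inflation of MBAT + iQuit vs MBAT needs separate groups, which no section states. A reader might also infer that the trial must grow beyond its maximum of 500. That too needs separate groups and a sizeable ICC, and it takes the plan's 80% as given.

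On make-up sessions, Section 5 says "if a group member is unable to attend a session they may make it up by watching the video recording". This reduces live contact, but the recorded session is still shared content, so its effect on the correlation cannot be settled from the documents.

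The adequacy sentence follows a reference to repeated measures and is correct for them. It needs limiting, not deleting. The general promise to test covariance structures does not help, since it operates inside a model already defined as time within subject.

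**Conclusion.** The point holds in conditional form. The design is partially nested, the primary model omits the group level, and nothing else in Section 9 supplies it. If the ICC is above zero, the planned standard errors are too small for MBAT vs UC (slightly) and for contrasts of an MBAT arm with text-only. For MBAT + iQuit vs MBAT they are too small with separate groups and slightly too large with shared, evenly mixed groups. iQuit vs UC is untouched.

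The size rests on assumed ICCs of 0.01 to 0.10 and three to four observed members per arm per group. On that basis the largest true error is 8.6%, and power for MBAT + iQuit vs MBAT in separate groups runs from about 79% down to 69-72%. Errors are larger only if separate groups are larger. This is worth correcting because a named hypothesis 1a contrast has an error of unknown direction and the remedy is cheap. It does not invalidate the trial.

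**What to change.** - Record an MBAT group identifier, and state in Section 5 whether the two MBAT arms share groups.
- In Section 9 (Aim I), add a random group intercept that operates only in the two MBAT arms. Use group-based small-sample degrees of freedom for MBAT vs UC, and for MBAT + iQuit vs MBAT if groups are separate. If groups are shared, that contrast is within group and should use participants-within-groups degrees of freedom.
- Prespecify what happens when the group variance is estimated at zero, for example keeping the same degrees of freedom. In simulation this occurred in about 57% of trials at ICC 0 and 20% at ICC 0.05.
- If a GEE is wanted (group as cluster, UC and text-only participants as singletons, small-sample-corrected variance), name it in advance as a sensitivity analysis or fallback. State that its odds ratio is population-averaged, whereas the mixed model's is subject-specific.
- Carry group into the imputation model, and resample whole MBAT groups in the Aim II bootstrap.
- Limit the adequacy sentence to the repeated measures.
- In the sample-size paragraph, state the power left at 485-500 under an assumed ICC and group size. There is no need to enrol more.

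The cost is wording, one stored variable and some code; group membership should be recoverable because sessions are scheduled and recorded. If the ICC is truly zero, simulated power for MBAT + iQuit vs MBAT falls from 82.1% (planned model) to 80.8% (GEE) or 79.6% (three-level model), a loss of 1.3 to 2.5 points. Intervals for MBAT contrasts would be slightly wider.
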